The objective of this study is to evaluate the effect of HBOT on subsequent airway complications in lung transplant recipients with evidence of ischemic changes in the large airway epithelium. Study subjects with extensive desquamation (exudative plaques) of the large airway epithelium in the early post-transplant period will be randomized to HBOT or usual care and followed clinically for 12 months following randomization. We hypothesize that HBOT will decrease the number of airway complications in the treated subjects.

SUBJECT ENROLLMENT

Standard post-lung transplantation care includes a bronchoscopy with transbronchial lung biopsy at 1 month after surgery. We believe that it is in this early period, when the neovascularization of the large airways is thought to occur, that subjects are most likely to benefit from HBOT. Patients who are noted to have extensive exudative plaques (grade 3 or 4) at their 1 month bronchoscopy will be referred for a standard follow-up bronchoscopy 2 to 3 weeks later. Should the patient show no sign of improvement in their airways, or worsening of the plaques they will be considered eligible for enrollment in the study.

Exclusion Criteria

Exclusion criteria include: use of mechanical ventilation with FiO₂ greater than 40%, use of extracorporeal membrane oxygenation, use of inhaled nitric oxide, presence of pneumothorax, pregnancy, or inability to provide informed consent. In addition, subjects who are deemed to be

too clinically unstable to be transported safely to the hyperbaric facility by their treating physicians will be excluded from enrollment.

Randomization

Once subjects are deemed eligible for enrollment, they will be questioned as to their interest in participating in the study by the treating physician. Those interested will be approached by the study coordinator for informed consent. Once informed consent is obtained, subjects will be randomized to usual care or HBOT by selection of a pre-prepared envelope containing the randomization assignment. We will target a total enrollment of 40 subjects with 1:1 enrollment to either HBOT or usual care.

Subject Compensation

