Subjects will not be compensated for participation in the study. However, they will not be charged for hyperbaric treatment or the research biopsies. The airway and rejection surveillance bronchoscopies are part of current standard care in the Duke lung transplant program and are continued accordingly in the study. All participants will be recruited at DUHS.

STUDY PROCEDURES

Hyperbaric Therapy

The HBOT will be performed with the standard HBOT protocol used at Duke for the treatment of compromised grafts and flaps. This is 2 hours of breathing >99% medical grade oxygen inside an air-pressurized chamber at 2 ATA once a day for 20 sessions. These sessions will be scheduled 3-5 times per week, depending on the availability of the patient and the hyperbaric medicine physician. The HBOT procedure used for this study will be identical to that used for clinical practice in the Duke University Health System Center for Hyperbaric Medicine and Environmental Physiology, including the oxygen that is used in the chamber. Patients will receive treatment through the regular clinical hyperbaric service. These are routine, not special, treatment sessions and they will receive them alongside other Duke University Medical Center patients being treated for other reasons. The medical grade oxygen used is a part of the Duke University Health System Center for Hyperbaric Medicine and Environmental Physiology hyperbaric chamber system.

The patients sign the standard Duke informed consent for the administration of HBOT inside the chamber. The primary risks, which each occur in less than 10% of patients, are middle ear barotrauma from the changes in barometric pressure (resolves in a few days) and temporary near-sightedness that may occur after 20 to 30 sessions, and resolves in 2-3 months, but which can rarely leave some persistent myopia that requires a change in eyeglass prescription. The other

risks are very rare (<1%) and include oxygen-induced convulsions, and pneumothorax, and there is a very remote chance of mechanical or electrical failure in the chamber resulting in a fire.

Airway Surveillance

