While the patients randomized to receive usual care will not undergo HBOT, both study groups will receive standard serial bronchoscopies for airway clearance and for the collection of bronchoalveolar lavage fluid for culture data, due to the high rate of infection in lung transplant patients. All subjects will undergo the standard surveillance bronchoscopies every 3 to 4 weeks (x3) for clearance of the exudate from the airway, as well as monitoring progression of the airway abnormalities. Additional bronchoscopies will be performed as clinically indicated. Following the completion of the airway surveillance, subjects will revert to the standard rejection surveillance schedule of bronchoscopy every 3 months for the first year post-transplant.

At each surveillance bronchoscopy, subjects will have the standard bronchoalveolar lavage performed for detection of infectious agents. Due to the high evidence of airway infections in patients with severe exudative plaques, a lavage is performed during each bronchoscopy as a part of standard practice to collect microbiologic data. As participants in this study, an, endobronchial biopsy of the airway epithelium will be performed at the main carina to collect a sample of recipient epithelium as well as at the first subcarina for each donor lung. Three samples will be collected from each of the biopsy sites. These samples are small (1 to 2 mm) and are thought to have a minimal clinical risk of minor bleeding associated with the procedure. Biopsy will add roughly 3 minutes total to each procedure. These samples will be used for mRNA extraction to detect expression of genes associated with response to tissue hypoxia.

Measurements and Data Collection

Primary outcomes: Need for airway stent placement and rate of acute rejection in the 12 months of observation as determined by transbronchial lung biopsy.

Secondary outcomes: Include development of airway stenosis, need for balloon bronchoplasty, development of clinically significant pulmonary infection as defined by initiation of antimicrobials to treat the suspected organism, development of airway dehiscence following enrollment in the study, development of bronchiolitis obliterans syndrome, and bronchial epithelial gene expression.

Additional clinical data to be collected will include spirometric data, frequency of hospitalization, hospital days, ICU days, mechanical ventilation days, need for tracheostomy, and survival.

TREATMENT ARM CROSSOVER

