the large airways. Experience with HBOT in this population is limited, but rates of significant airway stenosis may be as low as 10% after therapy. Sample size calculations using a 60% stenosis rate in the usual care group, a 10% stenosis rate in the HBOT group with a p-value of 0.05 suggest that a sample of 14 subjects/group will have an 80% power to detect statistical significance. We will target a total of 40 subjects to allow for subject withdrawal and loss due to the development of critical illness in this tenuous population. Intention to treat analysis will be used for all patients based on initial randomization, with subgroup analysis for the crossover patients for airway stent placement. All biologic samples will be collected by week 6, prior to any patient crossover events.

DATA and SAFETY MONITORING

Data will be stored on a secured Access database located on the PIN station “U” drive in an secured folder. All subject entries will be de-identified using a study assigned identification number. The key to the study identifiers will be kept in a locked file cabinet in the study coordinators office. Database use will be limited to the primary investigators, co-investigators, and the study coordinator.

Primary risks are related to bronchoscopy with minimal risk of bleeding related to the endobronchial lung biopsy, and some discomfort from the bronchoscopy itself which is part of usual post-transplant care. Additional risks of hyperbaric treatment are detailed above and very rare. Any adverse events that occur during the study will be immediately reported to the IRB.

Table 1. Pseudomembrane Scoring System

Stage	Definition
Stage 0	No exudate
Stage 1	Limited to anastomosis
Stage 2	Anastomosis to upper lobe orifice, including medial bronchus intermedius
Stage 3	Involvement of the lower lobe orifice
Stage 4	Covers all visible airways

REFERENCES:

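### Acute rejection is a primary outcome read from biopsy in a trial without a sham, and nothing in the plan keeps the arm from the reader; the risk can be reduced at little cost

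*Combined protocol and SAP*

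**What the plan says.** The section Measurements and Data Collection lists two primary outcomes: the need for an airway stent, and the "rate of acute rejection in the 12 months of observation as determined by transbronchial lung biopsy". It does not name who reads the biopsies or the grading criteria. It also does not say whether a patient counts once (any rejection) or the rate is per biopsy.

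Allocation is by envelope (Randomization): "subjects will be randomized to usual care or HBOT by selection of a pre-prepared envelope containing the randomization assignment". The control condition has no chamber sessions (Airway Surveillance): "While the patients randomized to receive usual care will not undergo HBOT, both study groups will receive standard serial bronchoscopies". The protocol does not use the term open-label, but patients and treating staff will know the arm.

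Two statements bear on how the arm could reach a reader. Under Hyperbaric Therapy: "Patients will receive treatment through the regular clinical hyperbaric service". Under Subject Compensation: "The airway and rejection surveillance bronchoscopies are part of current standard care". Both the treatment and the biopsies therefore run through ordinary clinical channels.

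The only identity safeguard is under Data and Safety Monitoring: "All subject entries will be de-identified using a study assigned identification number". It covers database entries, not the reading of slides. No section describes masking of any person at any step.

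**The concern.** Grading rejection on a transbronchial biopsy is a judgement. Where the comparator has no sham and the judgement feeds a primary outcome, a reader who knows the arm may grade differently by arm, and the difference could be created or hidden. With 20 patients per arm, a few patients graded differently are enough to matter.

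The two primary outcomes differ in what can be done. The treating team decides on a stent and cannot easily be kept unaware of the arm. A slide can be graded by someone who has not been told it, with no change to treatment. The outcome also covers 12 months of repeated sampling, so a small tendency at each reading could accumulate within a patient.

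**Working it through.** **Inputs from the protocol.** The target is 40 patients, 1:1, so 20 per arm (Randomization). Categorical data are compared by Fisher's exact test, and 0.05 is the significance level in the sample-size statement (Data Analysis and Statistical Considerations).

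**The plan's own figure.** The only design calculation is for airway stenosis, 60% against 10%, giving 14 per group at 80% power. It reproduces with the two-sided pooled normal formula without continuity correction:

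n = [1.96·√(2·0.35·0.65) + 0.842·√(0.6·0.4 + 0.1·0.9)]² / 0.5² = (1.322 + 0.484)² / 0.25 ≈ 13.04, rounded up to 14.

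It does not bear on this point, because the protocol gives no expected rate for acute rejection.

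**Assumptions for the illustration.** None of these is in the documents.
- The true rejection rate is the same in both arms, p = 20%, 30% or 40%.
- Each patient is recorded as yes or no.
- The test is two-sided at 0.05 with 20 analysed per arm.
- Reading adds d to the recorded rate in usual care and nothing in HBOT.

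**Calculation.** Let a and b be the numbers recorded with rejection in usual care and HBOT. The chance of a significant result favouring HBOT is the sum, over all pairs with a > b and Fisher p ≤ 0.05, of Bin(a; 20, p + d) × Bin(b; 20, p). The total false-positive rate adds the pairs with a < b.

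| Shift d | Patients of 20 | Favouring HBOT, p = 20% / 30% / 40% | Total, both directions, p = 20% / 30% / 40% |
|---|---|---|---|
| 0 | 0 | 1.1% / 1.2% / 1.2% | 2.3% / 2.5% / 2.4% |
| 5 points | 1 | 2.8% / 2.8% / 2.5% | 3.3% / 3.4% / 2.9% |
| 10 points | 2 | 6.1% / 5.7% / 4.7% | 6.2% / 5.9% / 4.9% |
| 20 points | 4 | 19.2% / 16.3% / 14.3% | 19.2% / 16.3% / 14.3% |

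The second column is d × 20.

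**Reading the table.** Fisher's test is conservative at this size: with no shift it rejects in only 2.3-2.5% of trials. A 5-point shift leaves the total below the nominal 5%, and a 10-point shift brings it to about 5-6%. Clear inflation needs a shift of around 20 points, that is, on average 4 of 20 usual-care patients over-called and none in the HBOT arm. A shift in the other direction would hide a benefit or suggest harm.

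**Accumulation over readings.** If knowledge of the arm added a 2% chance of a false rejection call per reading (assumed), a patient with 3 readings would carry 1 − 0.98³ ≈ 6%, and one with 6 readings 1 − 0.98⁶ ≈ 11%. The protocol does not fix the number of biopsies per patient, so both counts are assumptions.

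**The case against.** The strongest reply is that the protocol is silent on the reader; it does not show an unmasked one. A routine pathologist may never learn the arm. No section says that request forms state it or that the reader opens the clinical record. Usual-care patients may also be offered HBOT 8 to 12 weeks after the initial study bronchoscopy (Treatment Arm Crossover), so an entry for HBOT does not by itself reveal the randomized arm. All of this stands.

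A reader might infer from the investigators' stated optimism that slides would be graded in favour of HBOT. The documents do not support that. The Background reports encouraging experience with pseudomembranes, infections and airway stenosis, and the stated hypothesis concerns airway complications. The one link to rejection is a possible role of ischemia in chronic rejection, not acute rejection. These are also the views of the study group, and nothing identifies the slide reader as one of them. The direction modelled above is therefore an assumption.

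A reader might also infer that the damage could never be repaired. That is too strong: if slides are kept, on which the documents are silent, a masked re-reading would be possible later. Nor is masking free, since the reader gives up some clinical history.

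Finally, masked reading is only a partial remedy. Extra bronchoscopies are done on clinical indication by staff who know the arm, so biopsy frequency can differ between arms, and the stent outcome is untouched. This is correct, but it is no reason to leave open the part that is easy to close.

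**Conclusion.** The point holds as a gap in safeguards. A primary outcome that depends on a reader's judgement is compared against a control without a sham, and the plan keeps the arm from no one. The documents do not establish that the reader knows the arm, that the reader expects HBOT to lower acute rejection, or that the result will be biased. Size and direction are unknown.

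Under the assumptions listed, the illustration gives a modest effect for a 10-point shift (a false result favouring HBOT in 4.7-6.1% of trials, against about 1.2%) and a serious one for a 20-point shift (14-19%). These figures show how sensitive a 40-patient trial is; they do not estimate what would happen in this one. The case for acting is that the safeguard is small. If the reader is already unaware of the arm, writing it down makes the result more credible.

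**What to change.** Add to Measurements and Data Collection:

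- Transbronchial biopsies from study patients are sent under their normal clinical identifiers, on a request form that omits the study arm and HBOT.
- The usual pathologist records the rejection grade before consulting any record of the arm.
- That grade is the one used for the primary outcome.
- Any release of the arm that is needed for care is logged.

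Normal identifiers are preferable to the study number. These are standard-care specimens, and the key to the study numbers is locked in the coordinator's office, so results sent under a study number would have to be re-linked before they could be used for care.

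Also state that the number of transbronchial biopsies per patient will be reported by arm. Masked reading does not address unequal sampling, and this report would make it visible.

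The cost is a short protocol addition and a request-form instruction. Reader, slides, timing and sample size stay the same. The reader has slightly less clinical history unless it is requested, and the safeguard relies on the reader following the instruction.

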EFFECT OF HYPERBARIC OXYGEN THERAPY ON THE DEVELOPMENT OF AIRWAY STENOSIS IN PATIENTS WITH SEVERE AIRWAY EXUDATIVE PLAQUES EARLY AFTER LUNG TRANSPLANTATION

[name], [name], [name]

NCT02363959

BACKGROUND:

Central airway stenosis (CAS) is seen in 8-15% patients after lung transplantation.^{1,2} Development of airway stenosis can cause decline in pulmonary function, increased respiratory symptoms, increased infections, and occasionally death³. The lungs are unique in containing dual circulatory supply from the pulmonary circulation which is reanastomosed during lung transplantation, and the bronchial circulation which is not. Perfusion of the large airways is thought to occur via retrograde flow from vascular plexus' between the bronchial and pulmonary arterial circulation until new collateral circulation to the bronchial arterial system can develop in the weeks following transplantation³. Assessment of large airways perfusion has been surprisingly poorly studied, but development of airways ischemia post-transplantation is thought to be involved with development of CAS and other airway complications, opportunistic infections, particularly fungal infections, and possibly with chronic allograft rejection.^{1,4}

CAS is managed with balloon dilation followed by airway stent placement for recurrent stenosis.⁴⁻⁷ A limited number of retrospective studies have shown that the treated airway complications do not affect survival.^{1,8} However, these airway complications prolong mechanical ventilation, hospital and ICU length of stay, increase cost, and adversely affect quality of life³.

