Should patients enrolled in the usual care arm develop airway complications such as airway stenosis, dehiscence, or airway malacia, or if the patient fails to improve their exudative plaque score over the period of observation, they may be offered hyperbaric therapy with continued collection of clinical data. Subjects will be eligible for crossover therapy between 8 and 12 weeks after the initial study bronchoscopy.

There are two criteria for a patient to qualify for HBOT crossover treatment. The first criterion is the development of an airway complication, most likely airway stenosis requiring intervention. This is clinically defined by our group as an airway that is no longer traversable with a therapeutic (6.4mm OD) bronchoscope. Other complications are airway dehiscence or malacia (excessive loss of structural integrity). The second criterion is failure of the airway exudate to improve in score severity during the 8 week observation period. This is measured using the scoring system outlined in Table 1.

RISK/BENEFIT ASSESSMENT

It is currently unknown if treatment of patients with severe exudative plaques in the early post-lung transplant period with HBOT will prevent development of large airway complications. Our limited anecdotal experience suggests it may improve outcomes. The risks of the procedure are small and detailed above. The potential benefits are significant since airway stenosis can lead to worse allograft function, increased infections, and occasionally death. Subjects randomized to usual care will be at usual risk of airway complications. Given the clinical equipoise regarding HBOT treatment in lung transplant, we feel this is an ethical treatment decision for this patient population.

COST TO THE SUBJECT

There will be no additional costs to the subject over usual care. The hyperbaric treatment will be provided at no charge to the subjects.

DATA ANALYSIS AND STATISTICAL CONSIDERATIONS

Data analysis will be performed by the primary investigators. Categorical data will be analyzed using Fisher's exact test given the small sample size, while continuous data will be assessed for statistical significance with Student's t-test. Our prior work with airway stenosis in lung transplant recipients documented a 15% rate of stenosis in all transplant patients. Our clinical experience suggests a rate 2 to 4-fold higher in patients with severe ischemic desquamation of

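### Does the plan need a written rule for counting hospital, ICU and ventilation days in patients who die or leave before 12 months?

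*Combined protocol and SAP*

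**What the plan says.** Measurements and Data Collection names primary outcomes, then secondary outcomes, and then a third group of data simply to be collected. That group ends with "hospital days, ICU days, mechanical ventilation days, need for tracheostomy, and survival". No counting window or denominator is attached to the day counts, and nothing is said about death or early exit.

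Four other statements bear on the point:

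- Objectives: patients are "followed clinically for 12 months following randomization".
- Data Analysis and Statistical Considerations, on the test: "continuous data will be assessed for statistical significance with Student's t-test".
- The same section, on the analysis set: "Intention to treat analysis will be used for all patients based on initial randomization".
- The same section, on size: "a sample of 14 subjects/group will have an 80% power", followed by "We will target a total of 40 subjects to allow for subject withdrawal and loss due to the development of critical illness". No expected loss rate is given.

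Background explains why the counts are of interest: "these airway complications prolong mechanical ventilation, hospital and ICU length of stay, increase cost".

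**The concern.** A t-test needs one number per patient, and the plan does not define that number when follow-up is cut short. Intention to treat fixes the arm in which a patient is counted, not the days entered for someone who was followed for three months. Survival is collected, but nothing links it to the day counts.

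At least three rules can be defended: days up to exit, completers only, or days scaled to 12 months. They can give different answers. Under the first, an early death can pass for a short stay. The plan also names critical illness as a reason for loss, and critical illness is a likely source of ICU and ventilation days, so losses may be related to the quantity being counted. The primary investigators do the analysis, and a rule chosen after seeing the data would weaken a comparison that Background invites readers to treat as evidence on the burden of airway complications.

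**Working it through.** **1. The plan's own figure.** Inputs from Data Analysis and Statistical Considerations: "a 60% stenosis rate in the usual care group", 10% with hyperbaric oxygen, alpha 0.05, power 80%. The two-sided pooled formula, with mean rate 0.35, gives

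n = [1.96 × √(2 × 0.35 × 0.65) + 0.842 × √(0.6 × 0.4 + 0.1 × 0.9)]² / 0.5² = 13.04, rounded up to 14 per group.

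The stated 14 is reproduced (power 83.0% at 14 per group).

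**2. What the surplus means.** 40 - 2 × 14 = 12, or 30% of 40. This is spare enrolment for the stenosis comparison and depends on the formula used. With the planned Fisher's exact test, two-sided, 17 per group are needed to pass 80% (82.7%), and the surplus is 40 - 34 = 6. Neither figure predicts how many day counts will be incomplete. A critically ill patient may still have hospital and ICU days recorded.

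**3. Size of the effect on raw totals (assumed inputs).** Suppose both arms truly have 30 hospital days per patient-year, days accrue evenly, and lost patients leave at mid-year on average. The arm mean with L of 20 lost is (1 - L/20) × 30 + (L/20) × 15.

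| Lost per arm | Means | False difference |
|---|---|---|
| 6 vs 6 | 25.5 and 25.5 | 0 |
| 2 vs 6 | 28.5 and 25.5 | 3.0 |
| 0 vs 6 | 30.0 and 25.5 | 4.5 |

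Balanced losses lower both means equally. Only unbalanced losses create a difference.

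**4. Do the three rules disagree?** Simulation, all distributions assumed: 20 per arm, no treatment effect, 20,000 trials per scenario. Days are log-normal with 20% or 50% zeros, median 10 when not zero, and log-SD 0.8 or 1.2. Exit is uniform over the year, with days accruing evenly.

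- Equal losses of patients like the rest: the rules differ on which arm has fewer days in 8-10% of trials with 4 losses in total, and in 18-20% with 12.
- Equal losses of sicker patients (no zeros, three times the median): 21-26% and 35-41%.
- Across these scenarios at least one rule reaches p<0.05 in 4-7% of trials. Disagreement in sign together with any p<0.05 occurs in at most 0.1% (patients like the rest) or 0.2-0.7% (sicker patients).

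With a true difference of zero, most sign disagreements are estimates falling on either side of zero by chance.

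**5. Unequal losses of sicker patients, 4 vs 8.** The full 12-month gap between arms is 6.1-9.2 days. Days to exit show 2.0-3.5, completers about 0, and scaled days 5.8-8.7. Scaling does well here because the simulation assumes even accrual, which is the assumption that scaling itself makes.

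**6. The opposite accrual pattern.** Suppose all of a lost patient's days fall before an exit time U that is uniform over the year. Days to exit are then exactly right. Scaling, with follow-up floored at one month, multiplies them on average by

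E[1/max(U, 1/12)] = 12 × (1/12) + ln 12 = 1 + 2.485 = 3.5.

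Ten true days become about 35. The ranking of the rules reverses.

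**7. Deaths, assumed 5% vs 25%.** Patients who die accrue 0-50% of their days, plus the terminal days shown.

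| Terminal days per death | Arm with more deaths has lower mean | Significant in its favour (nominal 2.5%) |
|---|---|---|
| 0 | 59-67% | 2.8-6.4% |
| 5 | 49-58% | 1.4-3.2% |
| 10 | 37-52% | 0.6-1.6% |

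The direction depends on a quantity that the documents do not give.

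**The case for a change.** The best case for a change is that a rule costs two or three sentences, the plan itself foresees the losses, and writing the rule down removes a discretionary choice. With unequal losses of sicker patients the choice does matter for the estimate: in step 5 the completers-only analysis hides a gap of 6.1-9.2 days altogether.

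Part of this stands. No rule is written, the rules can diverge, and intention to treat does not settle the matter. But the argument shows that a detail is missing, not that a stated method gives a wrong result. The obvious candidate for a fuller rule, scaling to 12 months, is not clearly better than the simplest one: steps 5 and 6 give opposite rankings, and loss through critical illness makes clustering before exit plausible. A rule would also have to say whether patients who die enter the t-test, and showing their days up to death leaves that open. A completers-only analysis, the worst performer in step 5, fits poorly with a plan that keeps every patient in the analysis as randomized.

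**Conclusion.** No change to the plan is needed. This is a gap in the definition of third-tier data, which an analyst can fill from what the plan already provides: a 12-month window from randomization, analysis of all patients as randomized, and survival collected alongside. Days observed within that window, shown by arm beside deaths, losses and months of follow-up, let a reader see whether unequal follow-up could explain a difference.

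The consequence is limited. No primary or secondary conclusion depends on these counts. With equal losses the chance that some rule gives p<0.05 is 4-7%. Bias in the estimate needs unequal losses or deaths: in the even-accrual illustration it is 3.0 days for 2 vs 6 lost, on an assumed 30 days per year, and for deaths its direction is not fixed. All these magnitudes rest on assumed distributions, exit times and death rates. Only the sample size and the margins of 12 and 6 derive from the plan's own figures. The judgement would differ if the day counts became a primary or secondary outcome.

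### Fisher's exact test is valid but conservative at 20 per arm (maximum two-sided type I error about 2.5%); Boschloo's exact test holds the same 5% limit with equal or greater power

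*Combined protocol and SAP*

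**What the plan says.** Under Data Analysis and Statistical Considerations, the plan says "Categorical data will be analyzed using Fisher's exact test given the small sample size". The same section fixes the level and the size of the trial: "Sample size calculations using a 60% stenosis rate in the usual care group" and "a 10% stenosis rate in the HBOT group with a p-value of 0.05" lead to 14 per group for 80% power. Enrolment is then set at 40, allocated 1:1, to allow for withdrawal and critical illness. Sidedness is not stated.

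The section also gives a range for the usual-care rate. Earlier work "documented a 15% rate of stenosis in all transplant patients", and clinical experience puts the rate in the target population at 2 to 4 times that, so 30% to 60%. For HBOT, "rates of significant airway stenosis may be as low as 10% after therapy".

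Measurements and Data Collection lists the outcomes that the test will serve: "Primary outcomes: Need for airway stent placement and rate of acute rejection in the 12 months of observation". Most of the secondary outcomes, such as stenosis, balloon bronchoplasty, infection, dehiscence and bronchiolitis obliterans syndrome, are also naturally yes/no. No rate is assumed for stent placement.

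**The concern.** The plan chooses Fisher's test because the sample is small, and a small sample is where the test is most conservative. It conditions on both margins of the table. With 20 per arm, the attainable p-values for a given total number of events are few and widely spaced, so the largest one not above 0.05 is often well below it. The unused error rate is lost power.

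Other exact tests do not condition on the total number of events and still guarantee the 5% limit. Boschloo's test takes Fisher's p-value as its statistic and maximises the tail probability over the unknown common event rate. Because Fisher's p-value is itself valid, Boschloo's p-value can never exceed it, so no rejection is lost. In a trial limited to about 40 patients and judged mainly on yes/no outcomes, some results could be reported as non-significant that an equally rigorous 5% test would call significant.

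**Working it through.** **Inputs.** From the plan: level 0.05; usual-care stenosis 60% for design, with a range of 2 × 15% = 30% to 4 × 15% = 60%; HBOT 10%; 14 per group; 40 in total, 1:1. Assumed: two-sided testing and, unless stated otherwise, exactly 20 per arm.

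**Step 1: the plan's own figure.** Pooled-variance normal approximation without continuity correction, with mean rate (0.60 + 0.10)/2 = 0.35:

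n = [1.960·√(2·0.35·0.65) + 0.842·√(0.60·0.40 + 0.10·0.90)]² / 0.50² = (1.322 + 0.483)² / 0.25 ≈ 13.04, rounded up to 14.

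The 14 per group is reproduced. It comes from an approximation, not from the planned test.

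**Step 2: type I error at 20 against 20.** There are 21 × 21 = 441 possible tables. Let R be the set that a test rejects at 0.05. Its size at common rate π is Σ over R of Bin(x; 20, π)·Bin(y; 20, π), maximised over π.

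| Test | Tables rejected | Maximum size | Size at π = 20% |
|---|---|---|---|
| Fisher | 214 | 2.53% (near π = 0.34) | 2.3% |
| Boschloo | 234 | 4.64% | 4.4% |

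Boschloo rejects all 214 of Fisher's tables and 20 more. Three outcomes as examples: 8/20 against 2/20 gives p = 0.065 (Fisher) and 0.039 (Boschloo); 6/20 against 1/20 gives 0.091 and 0.046; 12/20 against 5/20 gives 0.054 and 0.030.

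**Step 3: power at 20 against 20.** The same sum, with the usual-care rate for x and 10% under HBOT for y.

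| Usual care | Fisher | Boschloo | Gain (points) |
|---|---|---|---|
| 60% | 90.8% | 94.1% | 3.2 |
| 55% | 83.9% | 89.3% | 5.4 |
| 50% | 74.2% | 82.2% | 8 |
| 45% | 62.4% | 72.6% | 10 |
| 40% | 49.2% | 60.9% | 12 |
| 35% | 36.1% | 47.6% | 11.5 |
| 30% | 24.2% | 33.9% | 9.7 |

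At lower rates the gain is smaller: 4.6 points at 20% against 5%, and 1.5 points at 15% against 10%.

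**Step 4: unequal arms (usual care first).** At 20 against 19, Fisher's maximum size rises to 3.6% and Boschloo's is 4.2%. The gain is 0.5 points at 60% against 10%, 0.1 at 40% against 10% and 0.0 at 30% against 10%. At 20 against 18 the gains at the same three pairs are 2.5, 5.7 and 3.3 points.

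**Step 5: 14 per group, 60% against 10%.** Two-sided Fisher has 74.2% power and Boschloo 80.7%. Fisher needs 17 per group to pass 80% (78.6% at 16, 82.7% at 17). If the plan meant a one-sided test at 0.05, Fisher at 14 per group would also have 80.7%.

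**The case against.** Fisher's test is standard, widely understood, and keeps the type I error below 0.05. Conditional against unconditional inference is a long-standing methodological choice, so naming Fisher is not a mistake. If all 40 patients are retained in equal arms, it still has 90.8% power at the one effect that the plan specifies. All of this stands, and it makes the point one of efficiency.

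A reader might infer that every yes/no comparison, stent placement included, loses 8 to 12 points of power. The documents do not support that. The loss is about 3 points at the plan's own 60% against 10%, falls at low event rates, and almost disappears at 20 against 19. That last case is realistic: 40 is a target, allocation is by envelope with no blocking described, and losses are expected. For stent placement there is no assumed rate from which to compute a loss.

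A reader might also conclude that results significant at 5% will certainly be missed. Only 20 of the 441 tables change verdict at 20 against 20, so they may be missed.

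Finally, the plan has two primary outcomes and many others, with no multiplicity adjustment stated. Running each test closer to 5% raises somewhat the chance of at least one false positive. That is a real, modest cost. What remains is that Boschloo's test holds the same 5% limit for each comparison and gives up no rejection that Fisher would make.

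**Conclusion.** The point holds as an efficiency improvement. Two-sided Fisher at exactly 20 per arm has a maximum type I error of about 2.5%, against 4.6% for Boschloo. With 10% under HBOT, the power given up is about 3 points at 60% in usual care and about 8 to 12 points at 30% to 50%, most of the plan's own range for stenosis. The figures rest on two-sided testing and on an equal split of all 40 patients. They are stenosis rates and should not be carried over to stent placement.

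The choice matters more if losses bring the arms down to the 14 per group for which the plan claims 80% power. There, under two-sided testing, Boschloo meets the stated figure and Fisher falls about 6 points short of it (80 − 74.2 = 5.8). Nothing here makes the planned test invalid.

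**What to change.** Before anyone compares outcomes by arm, amend the sentence on categorical data in Data Analysis and Statistical Considerations along these lines: *Two-arm yes/no outcomes will be compared with the two-sided Boschloo unconditional exact test at the 0.05 level, with the risk difference and its exact unconditional 95% confidence interval; Fisher's exact p-value will be reported as a sensitivity result.* This wording also settles the sidedness. Fisher's test can stay for any categorical variable with more than two levels.

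The cost is one sentence. The test is in standard software, and no patients, visits or data are added. There are two small downsides: clinical readers know the test less well, which reporting Fisher alongside addresses, and the chance of some false positive across the many unadjusted outcomes rises somewhat. The timing matters, because a change of test after outcomes have been seen by arm would not be credible.
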